## **7. ETHICAL AND REGULATORY CONSIDERATION**

The study involves collecting questionnaire data and does not pose any risk to the participants. The study team will be experienced and trained in explaining the study appropriately and sensitively to parents when they are approached for consent. The families of babies who are receiving cooling therapy are usually supported by appropriate health care providers including perinatal mental health psychologists, family support workers and clinicians. If the participation in the study causes distress to the participants, they will be able to contact the study team or contact the community midwifery team or General Practitioner to seek appropriate mental health support. If parents identify themselves as depressed during the study period or the perinatal depression questionnaire highlights depression, we will refer the participants to the General Practitioner or perinatal mental health team, whichever service is available locally.

The study will need the approval by the Health Research Authority and an NHS Research Ethics Committee. Confirmation of capacity and capability from participating Trusts will also be secured. The study will be conducted under the sponsorship of University of Bristol.

### **7.1. Assessment and management of risk**

Data will be held in the previously allocated secure server at the University of Bristol. We will anonymise the data and the master file linking the patient details with anonymised ID will be stored in secure computer file with the respective PIs and the CI.

### **7.3 Peer review**

The protocol was reviewed by an independent reviewer, who has the knowledge in the field and is familiar with the analysis described in the study.

### **7.4 Patient & Public Involvement**

This protocol was developed with input from the NIHR South West Research Design Service. We have discussed the design of the research with parents of cooled infants. The group agreed on the outcomes to be studied and have contributed to the design and content of the parent information

sheet. The participant information sheet was revised based on the suggestions from parents of babies who have undergone cooling therapy in the past.

### **7.5 Data protection and patient confidentiality**

All the investigators will comply with the requirements of the Data Protection Act 1998 with regards to the storage, processing and disclosure of personal information and will uphold the Act's core principles.

The study involves depersonalised data and the data will be maintained in secure servers. Chief investigator will be the data custodian.

### **7.6 Indemnity**

This study will be sponsored by the University of Bristol. The University has Public Liability Insurance to cover the liability of the University to research participants. In the event that something goes wrong and a participant is harmed during the research study there are no special compensation arrangements. If a participant is harmed and this is due to someone's negligence then they may have grounds for a legal action for compensation against Bristol University or the NHS Trust or one of the other parties to the research, but they may have to pay their own legal costs.

### **7.7 Access to the final study dataset**

The chief investigator will have access to the full datasets. Data analysis and appropriate sections of the datasets will be shared with co-investigators.

### **8. Discontinuation / withdrawal of Participants from Study**

Parents will have the right to withdraw themselves from the study at any time. Parents who wish to discontinue will be asked for permission for the study team to complete data collection and follow up. They may withdraw consent for any aspect of the study including future procedures and data collection. In addition, the treating clinician may discontinue a participant from the study at any time if they consider it to be in the best interests of the parent's health and wellbeing.

### **9. SAFETY REPORTING**

Parents of infants who undergo cooling therapy are the participants of the study and the infants undergo standard care. Given there is no intervention involved in the study for the parents, and parental participation is limited to filling in Edinburgh postnatal depression scale, mother-to-infant bonding scale and paternal postnatal attachment scale, no adverse event or serious adverse event recording or reporting will be conducted for this group. However, if the postnatal depression questionnaire scored above 13 and/ or the thought of harming was scored as either "sometimes" or "yes, quite often", we will refer the participant to the general practitioner or perinatal mental health team services, if they are available.

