## 4. SAMPLE SIZE AND RECRUITMENT

### 4.1 Recruitment

The number of cooled babies cared for in tertiary NICUs in the past years range between 15-20 babies per year. Recruitment will be from up to 6 centres. Doctors or nurses from participating centres will be identified and form a recruitment team under the supervision of the principal investigator. Initial approach to participants regarding the study will always be by a member of their direct care team. Following this, a member of the recruitment team will approach the parents of babies who had received cooling therapy as soon as possible after the clinical team have updated parents of the clinical status of their baby and the treatment plan. They will explain the aims and

content of the study, give the participant information sheet to the parents and give opportunity to ask questions. After sufficient time, parents will have a further opportunity to ask questions. If the parents decide to participate, informed consent will be obtained. Participation will be voluntary. An informed written consent will be obtained from both mother and father or secondary parental figure separately. If only one of the parents consent, they will still be able to participate in the study. In families with same sex parents, we will send the mother-infant bonding questionnaire to the female secondary parent at 8 weeks instead of the paternal postnatal attachment scale.

During COVID-19, most neonatal units are allowing one or both parents to visit their baby at a time to reduce the footfall within the unit and practice adequate physical distancing between people within the unit. The research team will approach whenever parents visit their baby. If the partner is absent when mother is consented, we will obtain mother's permission to approach their partner. We will not approach mothers or fathers who are separated from their babies. They will be approached for the study within 5-7 days of birth when they are with their babies. If either parent has coronavirus infection and not allowed to visit, we will endeavour to approach parents via their telephone number if it is deemed to be appropriate after consulting the clinical team looking after the baby.

If the baby dies after 7 days of age, local team will inform the central research team so that the 8 weeks questionnaires will not be sent.

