#### **4.2 Sample size**

We estimated there will be a minimum of 90 eligible sets of parents of cooled infants over 12 months. After excluding 10% due to infant mortality and a further 10% that decline participation or are not recruited due to possible lack of clinical team availability to approach the parents, we anticipate we will recruit 80% of the eligible families of cooled infants (72 families). With a conservative estimate, if a further 20% of the families are lost to follow-up at 8 weeks, we will have 58 families over 12 months. We will aim to recruit 50 families over 18 months to estimate the distribution of bonding, attachment, and postnatal depression scores in parents and associations of centres with different visiting restrictions during COVID-19.

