## 6. DATA ANALYSIS

Variables that influence the maternal infant bonding and paternal infant attachment including parental age, parity, psychiatric illness, intake of antidepressants, parental education, ethnicity,

socio-economic status and severity of encephalopathy and the implications and degree of COVID-19 restrictions will be summarised for the cohort. The central tendency and dispersion of maternal-infant bonding, paternal-infant attachment scores and postnatal depression scores will be presented as means with 95% confidence intervals for different levels of COVID-19 visiting restrictions by centres. Change in maternal infant bonding and depression scores from week 1 to 8 will be presented as mean or median difference using parametric or non-parametric tests depending on the distribution of the data. We will report the proportion of parents with depression (EPDS  $\geq$  13) at 5-7 days and 8 weeks postpartum. If the visiting restrictions are eased during the study, we will compare the postnatal depression and bonding scores between the restrictions and no-restrictions epochs accounting for the potential confounders.

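### The referral trigger in section 9 starts one point above the depression definition in section 6, so a parent scoring exactly 13 on the EPDS is counted as depressed but not referred on score

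*Protocol*

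**What the plan says.** Three places in the protocol bear on this point.

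- **Section 6 (Data Analysis)** fixes the reporting definition: "We will report the proportion of parents with depression (EPDS $\geq$ 13"), at 5-7 days and at 8 weeks. A score of 13 is included.
- **Section 7 (Ethical and Regulatory Consideration)** makes a general commitment without a number: "If parents identify themselves as depressed during the study period or the perinatal depression questionnaire highlights depression, we will refer the participants". The referral goes to primary care or to a local perinatal mental health service.
- **Section 9 (Safety Reporting)** says that adverse events will not be recorded, then makes referral the exception: "if the postnatal depression questionnaire scored above 13 and/ or the thought of harming was scored as either" of two listed response options. The score part of this trigger excludes 13.

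Section 7 also describes background support. Families are "usually supported by appropriate health care providers including perinatal mental health psychologists, family support workers and clinicians", and distressed parents may contact the study team, the community midwifery team or their general practitioner.

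**The concern.** The protocol uses two cut-offs for the same scale and does not explain the difference. The stricter one governs clinical action and the looser one governs reporting. Section 7 ties referral to the questionnaire indicating depression, and the only score-based definition of depression in the readable text is that of section 6. Read together, sections 6 and 7 promise referral at 13, while section 9 taken literally does not trigger it.

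Staff at up to six centres who need a number will take it from section 9, because section 7 offers none. A parent who scores 13, does not endorse the harm item at the listed levels and does not self-identify as depressed could then be missed. The protocol itself describes these parents as vulnerable. Because section 9 switches off adverse event recording, its referral rule is the main active safeguard in that section.

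**Working it through.** **Comparing the rules.** The EPDS total is a whole number.

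| Score | Depressed (section 6: 13 or more) | Section 9 score trigger (above 13) |
|---|---|---|
| 12 or less | no | no |
| 13 | yes | no |
| 14 or more | yes | yes |

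The rules disagree at one value, 13. If section 9 read 13 or above, they would agree everywhere.

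**How many parents score exactly 13.** The protocol gives no EPDS mean or SD. The assumed range is a mean m of 6 to 10 and an SD s of 5 to 6, under two distributions.

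- *Normal with continuity correction:* P(13) = Φ((13.5 − m)/s) − Φ((12.5 − m)/s). For m = 6, s = 5: Φ(1.5) − Φ(1.3) = 0.9332 − 0.9032 = 3.00%. For m = 10, s = 5: Φ(0.7) − Φ(0.5) = 0.7580 − 0.6915 = 6.66% (before rounding of the terms).
- *Negative binomial (right-skewed) with the same mean and SD:* p = m/s², r = m²/(s² − m). For m = 6, s = 5: p = 6/25 = 0.24, r = 36/19 = 1.895, P(13) = 2.08%.

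| Mean, SD | Normal | Negative binomial |
|---|---|---|
| 6, 5 | 3.00% | 2.08% |
| 6, 6 | 3.37% | 2.00% |
| 10, 5 | 6.66% | 5.43% |
| 10, 6 | 5.86% | 4.64% |

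A fine grid over the whole range gives 3.0% to 6.7% (normal) and 2.0% to 5.4% (negative binomial), so 2.0% to 6.7% combined. A mean outside the range can give more: normal with mean 12 and SD 5 gives Φ(0.3) − Φ(0.1) = 7.8%.

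**Counts.** Section 4.2 states "We will aim to recruit 50 families over 18 months". Section 4.1 allows one parent to take part alone ("If only one of the parents consent, they will still be able to participate in the study"), so the number of parents lies between 50 and 100. For 8 weeks, the planning assumption in section 4.2 ("if a further 20% of the families are lost to follow-up at 8 weeks") leaves 40 to 80.

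| Time point | One parent per family | Both parents |
|---|---|---|
| 5-7 days | 50 × 2.0%–6.7% = 1.0–3.3 | 100 × 2.0%–6.7% = 2.0–6.7 |
| 8 weeks | 40 × 2.0%–6.7% = 0.8–2.7 | 80 × 2.0%–6.7% = 1.6–5.3 |

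**Check against the one prevalence in the protocol.** Section 1 cites depression in nearly 21% of mothers of cooled babies at one week. The cut-off behind that figure is not stated. If it was 13 or more, solving for the mean that gives 21% at s = 5 and s = 6 puts P(13) at 3.5% to 5.3% across the two distributions. That is 50 × 3.5% = 1.7 to 50 × 5.3% = 2.6 mothers, the middle of the range above.

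**The case against.** The best counter-argument is that section 9 states a sufficient condition. It does not tell staff to withhold referral at 13, and section 7 already covers that score if its wording is read with section 6. On that reading both sections can be followed, and no parent is denied referral. This stands as a matter of logic. It does not remove the need for a correction, because section 7 reaches 13 only by inference, while section 9 supplies an explicit number that leaves 13 out.

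A second argument is that a research definition and a clinical action threshold serve different purposes and may differ. They may, but the protocol offers no rationale, and a referral threshold stricter than the reporting definition is hard to defend on welfare grounds. Loose wording is the likelier explanation.

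Third, the harm is conditional. It needs a score of exactly 13, no qualifying harm-item answer, no self-identification, and staff who act on section 9 alone. The usual-care support and contact routes in section 7 also remain, and the content of the study flowchart could not be read, so any threshold stated there is unchecked. All of this stands and limits the size of the problem. None of those routes, however, is set off by a total score of 13, and a screening score should not depend on the parent coming forward.

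**Conclusion.** The concern holds. The text contradicts itself at one score value: 13 counts as depression in section 6 and, by extension, for the commitment in section 7, but fails the score trigger in section 9. The mismatch itself needs no assumption beyond whole-number scoring.

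Its size does rest on assumptions. With the assumed means and SDs, about 1 to 7 parents at 5-7 days and about 1 to 5 at 8 weeks would score exactly 13. These are upper-leaning as counts of missed referrals, because parents reached through the harm item, self-identification or a generous reading of section 7 are not subtracted. No estimate, confidence interval or reported proportion is affected. The point should be fixed because it concerns participant welfare and the remedy is very small.

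**What to change.** In section 9, change the score condition from *above 13* to *13 or above*. Keep the harm-item and self-identification routes as they are. It would also help to put the same cut-off in section 7, so that the general commitment carries a number and the three sections agree.

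The cost is a phrase in section 9 (and one in section 7 if adopted), plus a few extra referrals to the general practitioner or perinatal mental health team: at most about 1 to 7 at 5-7 days and 1 to 5 at 8 weeks under the assumptions above. Sample size, data collection and analysis do not change.

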### **10. DISSEMINATION POLICY**

All co-applicants (and where appropriate collaborators) will take an active part in the preparing and reviewing of all manuscripts and reports generated during or as a result of this study. Results will be presented locally, at the national and international conferences followed by publication in a peer reviewed journal.

## 10. APPENDICIES

### 10.1 Appendix 1- Required documentation

*Curriculum vitae of Chief investigator*

### 10.2 Appendix 2 – Schedule of Procedures

ACTIVITY	START	DUR ATIO N	in Process												Complete													
			Nov 2020	Dec	Jan 2021	Feb	Mar	Apr	May	Jun	Jul	Aug	Sep	Oct	Nov	Dec	Jan 2022	Feb	Mar	Apr	May	Jun	Jul	Aug	Sep	Oct	Nov	Dec
Obtain NHS REC /HRA approval/ sponsorship	Nov 2020	4																										
Participant NICUs local approval	Jan 2021	2																										
Recruitment, data collection	Jan 2021	18																										
Data analysis	May 2022	5																										
Dissemination, publication	Sep 2022	4																										

### 10.3 Appendix 3 – Amendment History

Amendment No.	Protocol version no.	Date issued	Author(s) of changes	Details of changes made
	1.3
